9.3.1.2 Parts D, E, and F

This is the first time that VX-445 will be administered to subjects with CF. The TC regimen of VX-445/TEZ/IVA will be evaluated in Parts D and E because in vitro, the TC has shown high levels of efficacy and has shown to provide a greater increase in chloride transport than any of the dual combinations or individual compounds.¹¹ The safety of VX-445 monotherapy will be evaluated in Parts A and B in healthy subjects, and the safety of VX-445 in TC with TEZ/IVA will be evaluated in Part C in healthy subjects. A Phase 3 program for TEZ/IVA is ongoing. Parts D and E are designed to evaluate the safety and efficacy of VX-445 in TC with TEZ/IVA and to establish proof-of-concept in 2 populations of subjects defined by *CFTR* genotype (F/MF and F/F). Additionally, Part F will evaluate the safety and efficacy of VX-445 in TC with TEZ and VX-561 (a deuterated form of IVA) in subjects with F/MF genotypes, if conducted at the sponsor's discretion.

Efficacy has not been demonstrated for a corrector, potentiator, or any corrector/potentiator combination in subjects with F/MF genotypes. A Phase 3 study of TEZ/IVA in subjects with F/MF genotypes (Study VX14-661-107) was terminated following a planned interim futility analysis which showed that the combination of TEZ/IVA did not result in a pre-specified improvement in lung function. Because there is no effective treatment for this population, placebo is the control in Parts D1, D2, and F.

A potential for benefit was demonstrated for TEZ/IVA in subjects with the F/F genotype in Study VX11-661-101¹⁷, and a Phase 3 study of TEZ/IVA in subjects with the F/F genotype (Study VX14-661-106) demonstrated a clinically meaningful benefit across multiple endpoints.¹⁸ Therefore, TEZ/IVA is the active control in Part E.

Parts D1 and D2 include a second dosing period (Period 2) during which subjects will be administered TEZ/IVA (or dual placebo, for the placebo arm). Period 2 is included to enable a more thorough evaluation of exposure-response relationships for the TC during VX-445 washout.

The Washout Period of Part E is described in [Section 9.1.2.5](#).

Randomization for subjects in Parts D2, E, and F will be stratified as outlined in [Section 9.1.2.2.1](#).

9.3.2 Study Drug Dose and Duration

9.3.2.1 Parts A, B, and C

VX-445 Starting Dose

[REDACTED]

Using the lowest of the HED values (4.8 mg/kg), assuming a 60-kg human subject, and applying a default safety factor of 10, the maximum recommended safe starting dose is estimated to be approximately 28 mg/day. The selected starting dose of 20 mg for Cohort A1 [REDACTED]

[REDACTED]

Part A VX-445 Dose Escalation

The planned dose escalation scheme for Part A is shown in [Table 9-1](#). Dose escalation criteria for Part A (including the data that will be reviewed before initiating successive cohorts) are presented in [Section 9.7.1.1](#). Stopping criteria are presented in [Section 9.8.1](#). Dose escalation may be adjusted upward or downward based on safety, tolerability, and PK data from preceding dose group(s).

The decision to initiate successive cohorts and dose selection will be based on safety, tolerability, and available PK data from preceding cohort(s).

Cohort A7 VX-445 Dose Selection

The oral dose of VX-445 will be administered in Cohort A7 as a tablet fasted versus fed, which will be selected based on emerging PK data from Part A. The oral dose will not exceed a dose shown to be safe and well tolerated in a previous Part A cohort. The planned IV dose of 20 mg was selected so as not to exceed the exposure cap or exposure levels expected following oral doses in Part A. [REDACTED]

[REDACTED] The IV dose may be adjusted pending data from previous Part A cohorts, but will not be predicted to exceed the highest exposure that was safe and well tolerated. If data to support use of the IV dose is not available, the IV dose will not be administered.

Part B VX-445 Starting Dose and Dose Escalation

The starting dose in Part B will be selected based on safety, tolerability, and PK data in Part A. The total daily dose in Cohort B1 will be at least 1 dose level below the highest Part A dose for which safety, tolerability, and PK results are available and that is safe and well tolerated.

Initiation of successive cohorts and dose selection will be based on safety and PK data as described in [Section 9.7.1.2](#).

Part C VX-445 Starting Dose and Dose Escalation

Part C may be initiated while Parts A and B are ongoing after review of safety, tolerability, and PK data.

The starting dose (Cohort C1) will be at least 1 dose level below the highest Part B dose for which safety and tolerability results are available and supportive. Dosing will be staggered in Cohort C1, with 2 subjects dosed (1 with VX-445 in TC with TEZ/IVA and 1 with triple placebo) at least 24 hours before the remaining 6 subjects. Staggering at higher doses may be conducted if deemed necessary based on review of emerging safety data.

Parts B and C Treatment Duration

The duration of dosing in Part B (10 days) and Part C (14 days) is a standard duration for multiple-dosing in first-in-human studies and is of sufficient length for an early assessment of safety and tolerability and for assessment of steady-state PK.

TEZ and IVA Doses (Part C)

The doses of TEZ and IVA are the same as those being evaluated in Phase 3 studies of TEZ/IVA combination therapy (TEZ: 100 mg qd; IVA: 150 mg q12h). These doses of TEZ and IVA are appropriate for evaluation in the TC based on in vitro experiments with VX-445 that evaluated similar levels of TEZ and IVA exposure after correction for protein-binding.

Administration of VX-445 with Food

Doses of VX-445 will be administered under fed conditions in all cohorts except Cohort A7, which includes a dosing period where VX-445 is also administered under fasting conditions to evaluate the food effect. Only a mild food effect is predicted for VX-445 oral absorption. However, given the ultimate intent to administer VX-445 in combination with TEZ/IVA, which are administered with fat-containing food, this early assessment of safety and PK will be conducted under fed conditions.

9.3.2.2 Parts D, E, and F

VX-445 Dosage

VX-445 will be given qd.

Part D may be initiated while Parts A, B, and C are ongoing after review of safety, tolerability, and PK data. Single doses of VX-445 up to 360 mg were safe and well tolerated in Part A, and multiple doses of VX-445 up to 340 mg qd for 10 days were safe and well tolerated in Part B. In Part C, multiple doses of VX-445 up to 280 mg qd in TC with TEZ 100 mg qd and IVA 150 mg q12h were safe and well tolerated after 14 days of dosing.

Part D1 will evaluate 1 dose level (mid-dose: 100 mg qd) of VX-445 in TC with TEZ/IVA to assess safety, tolerability, and PK in a smaller subset of subjects before enrolling a larger number

of subjects and evaluating a higher VX-445 dose. The mid-dose of VX-445 100 mg qd was selected to ensure a sufficient safety margin relative to nonclinical data and the clinical experience in Parts A, B, and C in healthy subjects, and is at least 1 dose level below the highest Part C dose for which safety and tolerability results are available and supportive.

Part D2 will evaluate 3 dose levels of VX-445 (low: 50 mg qd; mid: 100 mg qd; and high: 200 mg qd) in TC with TEZ/IVA. The TC-high dose of VX-445 does not exceed the highest dose shown to be safe and well tolerated in Parts A, B, and C.

The dose levels evaluated in Part D2 will be expected to provide clinical benefit (based on in vitro data) and will be selected to provide a range of exposure for exposure-response analyses of safety and efficacy.

The highest TC dose of 200 mg qd VX-445 used in Part D2 will also be used in Parts E and F. Dose- and exposure-response information obtained for the TC in Part D (subjects with F/MF genotypes) is expected to be applicable to other populations with an *F508del* mutation, including F/F, based on similar potency of the TC in HBE cells that have 1 copy or 2 copies of *F508del*.¹¹

TEZ Dosage

In all study parts, the TEZ dosage will be 100 mg qd, which is the same dose being evaluated in Phase 3 studies of TEZ/IVA.

IVA Dosage

In Parts D and E, the IVA dosage will be 150 mg q12h. This dosage is being used in Phase 3 studies of TEZ/IVA and is also the approved IVA monotherapy dosage for patients aged 12 years and older.

VX-561 Dosage

A VX-561 dose of 150 mg qd was selected for evaluation in Part F based on preliminary PK results from a relative bioavailability study (Study VX16-770-018) evaluating the 50-mg tablet formulation of VX-561. 150-mg qd is predicted to result in similar PK parameters as IVA when administered alone at a dose of 150 mg q12h, including AUC_{0-24h} and C_{trough} . The VX-561 dose selection accounts for differences in the PK profile relative to IVA. VX-561 has been dosed up to 225 mg qd for 7 days in a Phase 1 study.

Treatment Duration

The 4-week treatment duration for the TC is based on previous experience with CF correctors and potentiators in clinical studies of subjects with CF. In previous studies of TEZ and IVA, PD effects were observed within 4 weeks of treatment. In Study VX06-770-101, treatment with IVA for 4 weeks resulted in statistically significant within-group changes from baseline in $ppFEV_1$ as well as a trend toward clinically meaningful improvements in the respiratory domain of the CFQ-R; differences in biomarkers of CFTR activity (sweat chloride) between IVA and placebo groups were also demonstrated. Furthermore, in Study VX11-661-101 dose-dependent improvements in lung function were observed for TEZ/IVA after 4 weeks of treatment, with the 2 highest dose groups showing statistically significant improvement in lung function versus placebo.¹⁷ In both studies, improvements in sweat chloride and $ppFEV_1$ were observed during the first week of dosing, with most of the effect observed within 14 days. Given the increased in vitro response of the TC relative to TEZ/IVA, it is expected that the 4-week treatment duration

of VX-445 will be sufficient to observe differences between treatment arms with respect to efficacy and PD endpoints.

Administration of VX-445, TEZ, IVA, and VX-561 With Food

Oral doses of VX-445, TEZ, IVA, and VX-561 will be administered under fed conditions. This is consistent with how VX-445, TEZ, IVA, and VX-561 were administered in nonclinical studies, including the GLP toxicity studies. Only a mild food effect is predicted for VX-445 oral absorption.

9.3.3 Study Population (Parts D, E, and F)

The study will include subjects with F/MF and F/F genotypes. The inclusion of subjects with F/MF and F/F genotypes is based on in vitro data that indicate the potential for significant improvements in chloride transport for CF patients with 1 or 2 copies of *F508del* in response to treatment with TC.¹¹ Subjects homozygous and heterozygous for *F508del* will be evaluated in different parts of the study because of the potential for differences in the magnitude of treatment response across the 2 genotype categories, and also because of the differences in current standard of care (See [Section 9.3.1.2](#)).

9.3.4 Study Assessments

9.3.4.1 Parts A, B, and C

The majority of safety and PK assessments are standard parameters for Phase 1 clinical studies. Rationales for other safety, PK, and PD assessments are listed below:

4 β -hydroxycholesterol (Part B)

4 β -hydroxycholesterol is an endogenous marker for cytochrome P450 (CYP) 3A activity.²⁰ Evaluation of 4 β -hydroxycholesterol is increasingly being used to assess potential clinical CYP3A induction. In Part B, comparison of 4 β -hydroxycholesterol on Day 10 (predose) relative to baseline (Day 1 predose) will be used to evaluate potential induction of CYP3A by VX-445. Based on in vitro data, VX-445 is not expected to be an inducer of CYP3A.¹¹

Spirometry (Parts B and C)

Transient declines in lung function have been observed at initiation of treatment with another CFTR corrector that is not included in the current study (LUM).²¹ Although nonclinical toxicity results do not indicate a risk of lung function decline for VX-445, lung function, as assessed by spirometry, will be included in Parts B and C as a precautionary safety measure.

Continuous ECG Monitoring (Part A, with the exception of Cohort A7)

Evaluation of QTc in early phase clinical studies with a robust dose range can be used to evaluate a potential exposure-response (E-R) relationship for QTc, which may be used to replace the thorough QTc study for new drugs.²² Therefore, continuous ECG monitoring will be performed in subjects in Part A (with the exception of Cohort A7) for possible later extraction and high-precision QTc analysis of 10 ECG replicate measurements. The ECGs collected by continuous monitoring may or may not be analyzed for the purpose of E-R modeling, based on future development decisions for VX-445. If analyzed, a separate analysis plan will be created for the evaluation of the data. Results of the high-precision QTc analysis and E-R modeling will not be included in the clinical study report (CSR) but will be included in a separate report.

G6PD Activity Test

The G6PD activity test will be performed for all subjects at screening. [REDACTED]

9.3.4.2 Parts D, E, and F

All safety and PK assessments are common assessments for clinical studies, with the exception of the G6PD activity test to be performed at screening in this study (see G6PD activity test paragraph above in [Section 9.3.4.1](#)).

The PD and efficacy assessments are widely accepted and are relevant to the study of patients in CF. All assessments are consistent with those measured in the registration studies of IVA (Kalydeco) or LUM/IVA combination therapy (Orkambi).

9.4 Study Restrictions

9.4.1 Parts A, B, and C

In Part A (with the exception of Cohort A7), subjects will be confined for the first 4 hours after dosing on Day 1 during continuous ECG monitoring, except to use the bathroom. After this time, if the equipment setup allows, subjects may be ambulatory during the continuous ECG monitoring, but will not engage in strenuous activities. If ECG equipment does not allow ambulation, appropriate accommodations will be made by the study site to facilitate continuous monitoring (i.e., bedside urinals will be provided).

Subjects should also take appropriate measures to minimize exposure to UV-radiation (e.g., prolonged sunlight, tanning booths) from the Day 1 Visit through the Safety Follow-up Visit.

Other study restrictions are summarized in Table 9-4.

Table 9-4 Parts A, B, and C: Study Restrictions

Restricted Medication/Food/Activity ^a	Timing of Restriction	
	From (minimum)	To
Depo-Provera [®]	6 months before first study drug dose	Completion of Safety Follow-up Visit assessments
Tobacco- or nicotine-containing product	45 days before first study drug dose	Completion of Safety Follow-up Visit assessments
Other investigational drugs or devices	30 days or 5 half-lives before first study drug dose, or time determined by local requirements (whichever is longest)	Completion of Safety Follow-up Visit assessments
Hormonal methods of contraception (oral or patch) or hormonal replacement therapies	28 days before first study drug dose	Completion of Safety Follow-up Visit assessments
Prescription medications	14 days or 5 half-lives (whichever is longer) before first study drug dose	Completion of Safety Follow-up Visit assessments
Nonprescription medications	14 days or 5 half-lives (whichever is longer) before first study drug dose. Occasional, limited ibuprofen (≤ 800 mg/day) and acetaminophen (≤ 2 g/day) is allowed for pain.	Completion of Safety Follow-up Visit assessments
Herbal supplements, vitamins, or other dietary supplements	14 days before first study drug dose	Completion of Safety Follow-up Visit assessments
Grapefruit; grapefruit, apple, or orange juice; vegetables from the mustard green family (e.g., kale, broccoli, watercress, collard greens, kohlrabi, Brussels sprouts, mustard); and charbroiled meats	72 hours before first study drug dose	Until last PK sample is taken
Alcohol	Not more than 14 drinks/week for female subjects or 21 drinks/week for male subjects, where 1 drink equals 5 oz (150 mL) of wine, 12 oz (360 mL) of beer, or 1.5 oz (45 mL) of hard liquor, within 6 months before the Screening Visit and none from 48 hours before admission to the CRU	Completion of Safety Follow-up Visit assessments
Caffeine	24 hours before first study drug dose	Until last PK sample is taken
Strenuous exercise (e.g., heavy lifting, weight training, and aerobics)	96 hours before first clinical laboratory testing	Completion of Safety Follow-up Visit assessments

CRU: clinical research unit; PK: pharmacokinetic.

^a See [Section 9.5.1](#) for guidance on concomitant medications.

9.4.2 Parts D, E, and F

Subjects should take appropriate measures to minimize exposure to UV-radiation (e.g., prolonged sunlight, tanning booths) from the Day 1 Visit through the Safety Follow-up Visit.

9.4.2.1 Prohibited Medications

Table 9-5 lists prohibited medications. TEZ, IVA, and VX-561 are metabolized extensively via cytochrome P450 (CYP) 3A4. VX-445 has a low potential to be an inhibitor or inducer of CYP enzymes based on in vitro data but is metabolized by CYP3A4/5. Therefore, use of moderate and strong inducers and inhibitors of CYP3A, which have the potential to alter the exposure of VX-445, TEZ, IVA, and VX-561 will be prohibited. VX-445 is a potential inhibitor of the hepatic transporter organic anion transporting polypeptide 1B1 (OATP1B1). Therefore, sensitive substrates of OATP1B1, such as HMG-Co-A Reductase Inhibitors (“statins”) are prohibited during treatment. Commercially available CFTR modulators are also prohibited.

A non-exhaustive list of study prohibitions and cautions for medication will be provided in the Study Reference Manual.

Table 9-5 Parts D, E, and F: Prohibited Medications

Medication	Timing of Restriction	
	Start of Restriction	End of Restriction
Moderate and strong CYP3A inducers	None allowed within 14 days before the first dose of the study drug on Day 1	None allowed through the Safety Follow-up Visit
Moderate and strong CYP3A inhibitors (except ciprofloxacin)	None allowed within 14 days before the first dose of the study drug on Day 1	None allowed through the Safety Follow-up Visit
Sensitive OATP1B1 substrates	None allowed within 14 days before the first dose of the study drug on Day 1	None allowed through the Safety Follow-up Visit
CFTR modulators (investigational or approved, except for study drug)	Parts D and F : None allowed within 28 days before Screening	Parts D and F : None allowed through the Safety Follow-up Visit
	Part E : None allowed beginning on Day -28 Visit	Part E : None allowed through Day 57

Note: The use of prohibited medication by subjects with medical needs will be addressed on a case-by-case basis with the medical monitor.

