9.1.2.3 Run-in Period (Part E)

The Run-in Period of Part E is 4 weeks and is designed to establish a reliable on-treatment (TEZ/IVA) baseline for the Treatment Period (Period 1). Subjects will receive TEZ 100 mg qd/IVA 150 mg q12h during the Run-in Period. The first dose of TEZ/IVA will be administered at the Day -28 Visit. The last dose of TEZ/IVA within the Run-in Period will be administered on Day -1 (1 day before the Day 1 Visit).

Study eligibility for Part E subjects will be confirmed before the first dose of TEZ/IVA in the Run-in Period (on the Day -28 Visit). Subjects who prematurely discontinue TEZ/IVA during the Run-in Period will not be randomized or participate in the Treatment Period (Period 1), unless they rescreen and complete a 4-week Run-in Period ([Section 9.1.2.1.2](#)).

Study visits during the Run-in Period will occur as shown in [Table 3-7](#).

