9.10 Replacement of Subjects

Subjects who withdraw or are withdrawn before the first dose of study drug (Day 1 for Parts A, B, C, D, and F; Day -28 for Part E) may be replaced.

Subjects who withdraw or are withdrawn for nonsafety reasons during the study drug treatment periods may be replaced at Vertex's discretion.

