10 STUDY DRUG INFORMATION AND MANAGEMENT

Study drug refers to VX-445, TEZ/IVA, TEZ, IVA, VX-561, and their matching placebos.

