Parts A, B, and C: serum samples will be analyzed at the local laboratory for all female subjects.

Parts D, E, and F: serum samples will be analyzed at the central laboratory for all females of childbearing potential. Urine pregnancy tests will be performed at the site. The urine pregnancy test must be negative before the first dose of study drug (Day 1 for Parts D1, D2, and F; Day -28 for Part E). Additional pregnancy tests may be required according to local regulations and/or requirements.

Follicle-stimulating Hormone, Screening Period only (All Parts): Blood sample for FSH will be measured for any suspected postmenopausal female with at least 12 months of continuous

spontaneous amenorrhea. Serum FSH levels must be within the postmenopausal reference range of the performing laboratory to be considered postmenopausal.

G6PD Activity Test, Screening Period only (All Parts): Blood samples will be collected for the G6PD activity test, which will be performed in an established laboratory that runs the assay routinely. For Parts D, E, and F, the use of a local laboratory that routinely runs quantitative G6PD activity assays is acceptable as an alternative to the central laboratory.

Serology (Parts A, B, and C): HBsAg, HCV antibody, HIV-1 and HIV-2 Abs, and p24 antigen will be tested for.

Drug and Alcohol Testing (Parts A, B, and C): Opiates, methadone, cannabinoids, cocaine, amphetamines/methamphetamines, barbiturates, benzodiazepines, cotinine, and alcohol levels will be assessed by a blood or urine test; alcohol breath tests are acceptable alternatives for alcohol testing. Subjects may undergo random urine drug screen and alcohol testing if deemed appropriate by the investigator. Drug screen result must be negative for all subjects to receive study drug.

CFTR genotype, Screening Period only (Parts D, E, and F): *CFTR* genotyping will be performed for all subjects. If the screening *CFTR* genotype result is not received before randomization, a previous *CFTR* genotype laboratory report may be used to establish eligibility. Subjects who have been randomized and whose screening genotype does not confirm study eligibility must be discontinued from the study ([Section 9.9](#)).

Additional Evaluations: Additional clinical laboratory evaluations will be performed at other times if judged to be clinically appropriate.

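### In Part E the ban on CYP3A inducers and inhibitors starts 14 days before Day 1, but TEZ/IVA starts on Day -28, so half of the run-in dosing days lie outside it

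*Protocol*

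**What the plan says.** Protocol Section 9.4.2.1 explains the restriction by CYP3A metabolism. It bars "use of moderate and strong inducers and inhibitors of CYP3A, which have the potential to alter the exposure of VX-445, TEZ, IVA" and VX-561. Table 9-5 then sets the dates. The inducer row and the inhibitor row carry the same start, "None allowed within 14 days before the first dose of the study drug on Day 1", and neither is split by part. The CFTR-modulator row of the same table is split, and its Part E line reads "None allowed beginning on Day -28 Visit".

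Section 3 defines Day 1 as the first dose of VX-445 or its placebo. Part E subjects are on treatment before that. Section 9.1.2.3 states: "The first dose of TEZ/IVA will be administered at the Day -28 Visit". Section 10 counts this as study drug: "Study drug refers to VX-445, TEZ/IVA, TEZ, IVA, VX-561, and their matching placebos". Two other places date the first study-drug dose in Part E the same way. Section 9.10 (replacement) gives "Day -28 for Part E", and Section 11.7.2 requires a negative urine pregnancy test "before the first dose of study drug (Day 1 for Parts D1, D2, and F; Day -28 for Part E".

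Section 9.4.2.1 also says: "A non-exhaustive list of study prohibitions and cautions for medication will be provided in the Study Reference Manual". That manual is not among the documents.

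**The concern.** The stated reason for the ban applies from the first TEZ/IVA dose, but the ban opens two weeks after that dose. As the table is written, a Part E subject may take a moderate or strong CYP3A inhibitor or inducer together with TEZ/IVA during the first half of the run-in. The Part E line in the CFTR-modulator row suggests that the CYP3A rows were simply not adapted when the run-in was added.

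What is at stake is TEZ/IVA exposure and subject safety during those days. Under Table 3-7, chemistry and ECG are done at Day -28 and Day 1, and PK sampling begins on Day 1. The Day -14 Visit has only sweat chloride and spirometry, and subjects coming directly from at least 14 days of TEZ/IVA do not need it. AEs and medications are recorded throughout, but recording does not prevent the combination.

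The OATP1B1 row is not part of this point. Its reason is VX-445, which starts on Day 1.

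**Working it through.** **Inputs**

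- First run-in dose: Day -28, with a window of ± 1 day (Section 9.1.2.3; Table 3-7).
- Last run-in dose: Day -1, which the protocol places one day before Day 1, so there is no Day 0 (Section 9.1.2.3).
- Start of the CYP3A ban: 14 days before Day 1, that is Day -14 (Table 9-5).
- Part E screening: Day -56 to Day -29 (Table 3-7).

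**Day count**

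1. Run-in dosing days, Day -28 to Day -1: 28. This reproduces the protocol's 4 weeks (28/7 = 4).
2. Days under the ban, Day -14 to Day -1: 14.
3. Days outside the ban, Day -28 to Day -15: 28 - 14 = 14, and 14/28 = 50%.
4. First dose one day late (Day -27): 27 - 14 = 13, and 13/27 = 48%.
5. First dose one day early (Day -29): 29 - 14 = 15, and 15/29 = 52%.
6. Ban from the Day -28 Visit: 0 of 28 outside, and 0 of 27 or 0 of 29 at the window ends, because the ban moves with the visit.
7. Ban from 14 days before the first run-in dose: it starts at Day -28 - 14 = Day -42. Again 0 run-in days are outside. The 14 lead-in days (Day -42 to Day -29) lie inside the screening window.

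**Whether another rule covers Day -28 to Day -15**

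- *Exclusion criterion 14 (Section 8.2.2).* It refers to the window in Table 9-5. Part E eligibility is confirmed before the Day -28 dose, when that window has not yet opened. The confirmation at randomization uses the same window, so it does not reach back beyond Day -14.
- *Exclusion criterion 7 and the CF-stability condition of Section 9.1.2.4.* Between them they block entry to Period 1 after a change in sino-pulmonary therapy or an unstable CF regimen in the 28 days before Day 1. They do not concern drugs taken for other reasons.
- *The acute-illness condition of Section 9.1.2.4.* It looks back only 14 days from Day 1. A non-CF illness treated on Day -28 to Day -15 does not block entry.
- *Section 9.5.2.* It requires a stable CF regimen, and medical monitor approval for new long-term medication. A short course is not covered, nor is a non-CF drug already in use.
- *The sentence in Section 9.4.2.1 that prohibits these drugs.* It carries no dates; the table supplies them.

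What remains is mainly a short-course non-CF agent, or a non-CF agent stopped by Day -15.

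**The case against.** The strongest reply has four parts.

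1. **The text is ambiguous rather than permissive.** The prohibition in Section 9.4.2.1 has no date limit and no exception for Part E. Sections 9.10 and 11.7.2 place the first study-drug dose of Part E at Day -28, so criterion 14 could be read as a window before that day. This does not cure the gap. Table 9-5 says expressly that the dose meant is the one on Day 1. Even on the other reading, criterion 14 would screen use before Day -28, not a course begun during the run-in. The same ambiguity touches criterion 7, but the stability condition in Section 9.1.2.4 is tied to the Day 1 Visit and does not depend on it.

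2. **Fourteen days suits what Part E measures.** The run-in exists to give an on-treatment baseline. Section 9.1.2.2.1 accepts 14 days of uninterrupted TEZ/IVA for stratification, and Section 9.3.2.2 reports that most of the effect appeared within 14 days in earlier studies. SAP Section 7.3.2 (Parts D, E and F) centres the safety analysis on the Treatment Period. This stands, and it is why no bias of the baseline or comparison is claimed. It does not answer the section's own exposure rationale.

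3. **The consequence is small.** Part E has about 24 subjects and the remaining route is narrow. No exposure-toxicity threshold is given for TEZ/IVA. Extra laboratory tests and ECGs can be done when clinically appropriate (Sections 11.7.2 and 11.7.5.1). The absence of scheduled tests applies equally to the covered days. All of this stands as a limit on size.

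4. **The Study Reference Manual may settle it.** It may. The point therefore concerns the protocol text only, and says nothing about what sites would in fact allow.

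**Conclusion.** The concern holds. Both CYP3A rows of Table 9-5 omit Part E's run-in, and 14 of 28 run-in dosing days (50%; 48% to 52% with the visit window) fall outside a ban whose stated reason covers them. No other rule in the protocol closes the gap.

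The percentage counts calendar days and does not measure risk. The documents give no rate of use of such drugs, so the number of subjects affected cannot be estimated, and no size of harm is claimed. The conclusion rests on reading Day 1 as Section 3 defines it and on the table, not the undated sentence above it, setting the timing. It should be corrected because the rule is wrong as written and the correction costs very little, not because it threatens the trial's results.

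**What to change.** In the inducer row and the inhibitor row of Table 9-5, keep the present start for Parts D and F and add a line for Part E.

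- **Preferred:** no use from 14 days before the first study-drug dose of the Run-in Period (the Day -28 Visit). This gives Part E the same lead-in that Parts D and F have. Tying it to the Run-in Period keeps it correct for subjects from Study 661-110, who arrive already taking TEZ/IVA.
- **Minimum:** reuse the Part E wording of the CFTR-modulator row, "None allowed beginning on Day -28 Visit". On the day count alone this is sufficient; the preferred line adds only the lead-in.

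Exclusion criterion 14 should follow whichever line is adopted. The OATP1B1 row stays at Day 1.

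The cost is one added line in each of two rows, with no change to visits, sample size or analysis. A few Part E candidates would have to stop such a drug earlier or be excluded. The table's note on case-by-case medical need still applies to them.
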